7.5 SECONDARY OBJECTIVE ANALYSIS

7.5.1 Key secondary objective analysis

This section is not applicable as no key secondary endpoint has been specified in the protocol.

7.5.2 Secondary objective analysis

All secondary endpoints in CTP, Section 2.1.3 will be analysed by using descriptive statistics and figures.

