Proprietary confidential information © 2025 Boehringer Ingelheim International GmbH or one or more of its affiliated companies

	
Estimated glomerular filtration rate (eGFR) < 30 mL/min/1.73 m² (CKD-EPI formula based on serum creatinine and cystatin C) at screening visit.QTc intervals (QTcF) greater than 450 ms in males or greater than 470 ms in females, or any other clinically relevant ECG findings (at the investigator's discretion) at screening visit.
Test product	BI 764198
dose	20 mg, 40 mg, 80 mg, and matching placebo, q.d.
mode of administration	Oral (p.o)
Comparator products	Matching placebo to BI 764198
dose	Not applicable
mode of administration	Oral (p.o)
Duration of treatment	12 weeks
Statistical methods	For the primary analysis, descriptive statistics will be provided. Proportion of patients achieving at least 25% UPCR reduction relative to baseline at 12 weeks will be described. In addition, an ANOVA model for the UPCR change from baseline at 12 weeks (and other endpoints as applicable) will be used to see difference across arms. The dose-response relationship based on reduction in log of UPCR will be explored using a graphical approach.

Clinical Trial Protocol

Proprietary confidential information © 2025 Boehringer Ingelheim International GmbH or one or more of its affiliated companies

FLOW CHART A – STUDY PROCEDURES

Trial Periods	Screening	Treatment Period						Follow-up
		1	2	3	4	5	EoT ²	
Visit ¹		1	2	3	4	5	EoT ²	FUP1
Week			0		4	8	12	13
Days from first dose	-30 ⁴	1 ⁵	4	29	57	85	92	115
Time window for visits (days)		0	+3	±3	±3	±3	±2	±3
Informed consent ⁶	X							
Demographics	X							
Height ⁷ , body weight	X			X	X	X	X	
Medical history	X	X						
Review of inclusion /exclusion criteria	X	X						
Physical exam ⁸	X			X		X		
Vital signs	X ²⁸	X	X	X	X	X	X	
12-lead ECG ⁹	X	X	X	X	X	X	X	
Sampling for safety laboratory (incl. serum creatinine/cystatin C for eGFR)	X	X	X	X	X	X	X	
Pregnancy testing ¹⁰	X	X		X	X	X	X	
Eye exams ¹¹	X					X ¹²		X ¹²
First morning void (FMV)	X							

Clinical Trial Protocol

Proprietary confidential information © 2025 Boehringer Ingelheim International GmbH or one or more of its affiliated companies

FLOW CHART A – STUDY PROCEDURES (cont.)

Trial Periods	Screening	Treatment Period						Follow-up
		2	3	4	5	EoT ²	FUP1	
Visit ¹	1							
Week		0		4	8	12	13	
Days from first dose	-30 ⁴	1 ⁵	4	29	57	85	92	115
Time window for visits (days)		0	+3	±3	±3	±3	±2	±3

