7.2.4 Secondary endpoint analyses

[figure not shown]
All secondary endpoints in Section [2.1.3](#) except pharmacokinetic parameters of BI 764198 will be analysed by using descriptive statistics and figures.

Further details will be given in the TSAP.

Clinical Trial Protocol

Proprietary confidential information © 2025 Boehringer Ingelheim International GmbH or one or more of its affiliated companies

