4. CHANGES IN THE PLANNED ANALYSIS OF THE STUDY

2) Two additional analysis sets were added to the list of Analysis Sets.

- The Per Protocol Analysis Set (PPS), consisting of all patients who were randomized and completed treatment with evaluable measurements of primary endpoint at both baseline and end of treatment visits within the residual period (5 days), has been included in the set of Analysis Sets analyzed in the trial.
The PPS is the analysis set used in the Sensitivity analysis.
- The Electrocardiogram Pharmacokinetic Concentration Analysis Set (ECGPCS) has also been added. This patient set includes all subjects from the Treated Set who provided at least one pair of a valid drug plasma concentration and a corresponding (i.e. time-matched) ECG endpoint to be used in the exposure-response analysis e.g. concentration-QT plots. For placebo subjects, the plasma concentration is set to zero and hence always considered as valid. The decision whether a time deviation between PK blood sampling and ECG recording is acceptable (and thus whether the pair of values were used) will be made no later than at the Report Planning Meeting (RPM) before database lock.

3) The CTP stated, as part of the primary analysis, that an ANOVA model, for the proteinuria (24-hr urine protein-creatinine ratio (UPCR)) change from baseline at week 12 (and other endpoints, as applicable), would be used to see the difference(s) across arms. However, an ANCOVA model with use of corticosteroid (CS) at randomization and baseline 24-hr UPCR, as covariates will be utilized instead. This

change was performed to align with the protocol study design that stratifies by CS use at randomization to ensure even distribution of patients taking CS across treatment groups, and to further control for any potential confounding effects related to CS use. Therefore, ensuring a more robust analysis.

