7.4 PRIMARY OBJECTIVE ANALYSIS

7.4.1 Primary analysis of the primary endpoint(s)

This is an exploratory trial. No confirmatory testing is performed and hence neither null nor alternative hypotheses are defined. Nominal p-values may be presented. The FAS will be used for the analysis of the primary endpoint.

An exploratory analysis for the primary endpoint, in terms of proportion of patients achieving at least 25% UPCR reduction relative to baseline at week 12 (patients missing the week 12, 24-hr UPCR will be counted as non-responders) will be conducted by providing 95% confidence intervals from each treatment group, via logistic regression utilizing corticosteroid use at randomization (variable CORTIC) and baseline 24-hr UPCR, as covariates. The baseline UPCR will be from the average of two 24-hour urine samples collected before visit 2 (before the first dose). Graphical representations of change in 24-hour UPCR from baseline will also be presented.

The primary estimand of interest is the treatment effect, assuming all subjects remained adherent to the assigned trial medication, and the study protocol using a hypothetical approach, i.e., study drug is taken as directed. This analysis will include all data collected until time of an ICE. For primary analysis, UPCR measurements after ICE will not be included. ICE and the strategies for handling intercurrent events are defined in the CTP section 7.2.2 and [section 6.3](#), above, as follows:

An intercurrent event (ICE) is defined as an event of,

[figure not shown]
- Early discontinuation,
- Lost to follow-up, or
- Death.

The strategies for handling intercurrent events in this trial are as follows:

- (1) Hypothetical estimand: assuming all subjects remained adherent to the assigned trial medication and the study protocol. This strategy will include all data collected until time of an ICE.
- (2) Treatment policy estimand: using all available data including data collected after an ICE.

For this analysis only the Hypothetical estimand will be considered.

In addition, an analysis of covariance (ANCOVA) model (for the UPCR change from baseline at week 12) will be used to see differences across arms, with corticosteroid use at randomization and baseline 24-hr UPCR, as covariates. Dose-response relationship based on reduction in log of UPCR may be explored using a graphical approach.

[figure not shown]

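### The urine secondary endpoints get no baseline- and stratum-adjusted comparison with placebo, and the plan leaves open which further endpoints its ANCOVA covers

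*SAP*

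**What the plan says.** The protocol synopsis (statistical methods) states that "an ANOVA model for the UPCR change from baseline at 12 weeks (and other endpoints as applicable) will be used to see difference across arms". SAP section 4 restates that scope, "change from baseline at week 12 (and other endpoints, as applicable), would be used to see the difference(s) across arms", and then replaces the model: "an ANCOVA model with use of corticosteroid (CS) at randomization and baseline 24-hr UPCR, as covariates will be utilized instead". Its reasons are the corticosteroid-stratified randomisation and a more robust analysis.

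Where the model is actually specified, it covers one variable. SAP 7.4.1 says "an analysis of covariance (ANCOVA) model (for the UPCR change from baseline at week 12) will be used to see differences across arms". Protocol 7.2.3 likewise names only the week-12 UPCR change.

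For the secondary endpoints, protocol 7.2.4 says that those other than the PK parameters "will be analysed by using descriptive statistics and figures". SAP 7.5.2 says "All secondary endpoints in CTP, Section 2.1.3 will be analysed by using descriptive statistics and figures". SAP section 7 lists the summary statistics for non-PK parameters as N, mean, SD, minimum, median and maximum.

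The urine secondary endpoints (protocol 2.1.3, SAP 5.2.2) are all changes:
- UPCR from visit 3 to week 12
- UPCR from baseline to week 13
- 24-hour urinary protein excretion from baseline to week 12

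SAP 6.7 defines a pre-dose baseline for every 24-hour urine endpoint as the average of two collections if available. Protocol 7.4 stratifies randomisation by corticosteroid use.

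**The concern.** The statements on scope do not meet. The synopsis and SAP section 4 suggest that the model reaches beyond the week-12 UPCR change, while the secondary-endpoint sections give no model at all. No visible text says which endpoints qualify.

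A reader who wants to compare a dose with placebo on these endpoints will have to subtract tabulated arm means, with no planned interval and no use of the stratum.

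The endpoints matter for interpretation. Week 13 is the off-drug measurement. Protein excretion has no creatinine denominator, which is useful because protocol 1.2 reports that the drug is believed to reduce tubular secretion of creatinine. Protocol 3.2 also names 24-hour proteinuria among the secondary endpoints by which efficacy will be further assessed.

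At 15 patients per arm, precision is scarce. The SAP already adjusts its own exploratory week-12 analyses for exactly these two covariates.

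**Working it through.** The plan gives no precision figure for the secondary endpoints, so there is none to reproduce. The 73.4% in protocol 7.5 concerns responder rates and does not enter here.

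**Inputs.** From the documents: 15 patients per arm, 60 in total, four arms (protocol 7.5), and two covariates (SAP section 4). Assumed, because the documents do not give them: the correlation r between baseline and follow-up, equal variances at both times, and complete data.

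**Step 1: variance of a dose-minus-placebo contrast.** Take the SD at each time as 1 and leave out the common factor 2/15.
- Unadjusted change: 2(1 − r)
- ANCOVA: 1 − r²
- Ratio: (1 − r²) / (2(1 − r)) = (1 + r)/2

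**Step 2: cost of estimating two covariates.** Multiply by about 1 + 2/(60 − 4 − 2 − 1) = 55/53 = 1.038.

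**Step 3: chance baseline imbalance.** The SE of the baseline difference between two arms is √(2/15) = 0.365 SD. With one such SE of imbalance, the change-score contrast is off by (1 − r) × 0.365 SD.

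| r | (1 + r)/2 | after covariate cost | SE reduction | equivalent patients per arm | left by a 1-SE imbalance |
|---|---|---|---|---|---|
| 0.5 | 0.75 | 0.778 | 11.8% | 19.3 | 0.18 SD |
| 0.7 | 0.85 | 0.882 | 6.1% | 17.0 | 0.11 SD |
| 0.8 | 0.90 | 0.934 | 3.4% | 16.1 | 0.07 SD |
| 0.9 | 0.95 | 0.986 | 0.7% | 15.2 | 0.04 SD |

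The SE reduction is 1 − √(third column). Equivalent patients is 15 divided by the third column.

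**Break-even.** (1 + r)/2 = 53/55 gives r = 0.927. Above about 0.93 there is no net gain.

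**Simulation check.** With 6,000 runs per value, 15 per arm and both covariates fitted, the variance ratios were 0.77, 0.86 and 0.97 at r = 0.5, 0.7 and 0.9. They are slightly lower than the table because the simulated stratum was split equally across arms and so cost almost nothing.

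**How often imbalance arises.** The probability that a given dose differs from placebo by more than 0.5 SD at baseline is 17%. For at least one of three doses it is 38%.

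**The case against.** Several points on the other side are sound and limit the finding.

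- A reader might infer that the plan dropped a promised analysis. It did not. The synopsis wording is conditional and names no endpoint, protocol 7.2.3 confines the model to the week-12 UPCR change, and SAP 7.5.2 follows protocol 7.2.4. What remains is an undefined qualifier. Redacted parts of the SAP may name other endpoints to which it refers, but 7.5.2 speaks of all secondary endpoints.
- A reader might infer that baseline imbalance goes uncorrected. A change score subtracts the reference value, so at r = 0.7 it already removes 70% of the imbalance, and stratification limits corticosteroid imbalance. What is left is ordinary sampling error, not bias: a 1-SE imbalance at r = 0.7 shifts the contrast by 0.110 SD, against an SE of 0.365 × √0.6 = 0.283 SD, or about 0.4 SE. The imbalance and the precision loss are largely one harm, not two.
- A reader might infer that these endpoints are the only support for the responder result. SAP 7.4.1 already gives an adjusted week-12 ANCOVA, protocol 7.2.3.2 a treatment-policy analysis, and SAP 6.4 a per-protocol set for sensitivity.
- Equal variances may flatter the gain. Baseline averages two collections and follow-up is one. Averaging reduces noise in the baseline, which moves the slope towards 1 and shrinks the advantage.
- The trial is non-confirmatory with no key secondary endpoint, so a descriptive approach to supportive endpoints is a legitimate choice.

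The last point does not dispose of the matter. The SAP adjusts its week-12 analyses in the same exploratory trial, and what is asked for is estimation, not testing.

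**Conclusion.** The point holds in a limited form. The scope of the ANCOVA is not defined, and the three urine change endpoints have no adjusted between-arm estimate or interval, although the covariates are in hand.

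The precision forgone is roughly 12% to 1% of the SE for r from 0.5 to 0.9. That range rests on an assumed r, equal variances and complete data, and the documents cannot narrow it. It also credits only the baseline covariate. If corticosteroid use predicts the change in proteinuria, the stratum term would add to the gain by an amount that cannot be sized here.

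The case for acting is that the improvement is nearly free and closes an ambiguity. The documents do not support calling the planned description biased or a broken commitment. The PK trough concentration is outside this point.

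**What to change.** In SAP 7.5.2, name the endpoints to which the section 4 model applies and add:

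- An ANCOVA with treatment, corticosteroid stratum and the pre-dose baseline of the same measure, for the week-13 UPCR change and the week-12 urinary protein excretion change. For the latter the covariate is baseline protein excretion, not the baseline UPCR named in section 4.
- A stated scale. Log is preferable, since the dose-response exploration already uses log UPCR. The contrasts then back-transform to ratios against placebo.
- If the visit-3-to-week-12 change is also modelled, pre-dose baseline UPCR as the covariate. The visit-3 value is taken after dosing has begun (day 4), so adjusting for it would condition on a post-randomisation measurement.
- Adjusted dose-minus-placebo estimates with nominal 95% confidence intervals, labelled exploratory, beside the descriptive tables.

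Align protocol 7.2.4 with the synopsis so that both state the same scope.

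The cost is a few lines of text, reuse of a model already planned, a few extra tables, and six more nominal contrasts (two endpoints by three doses), or nine if the visit-3 endpoint is included. No additional data are needed.

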7.7 EXTENT OF EXPOSURE

Descriptive statistics are planned for this section of the report based on the TS. The extent of exposure is calculated as drug stop date minus drug start date plus one day and treatment interruptions are not taken into account in the calculation.

Extent of exposure will be summarised using descriptive statistics (e.g. frequency, mean, SD, Min, median, and Max) in days

7.8 SAFETY ANALYSIS

All safety analyses will be performed on the TS, by treatment group. Placebo patients will be pooled in a single group.

7.8.1 Adverse Events

Unless otherwise specified, the analyses of AEs will be descriptive in nature. All analyses of AEs will be based on the number of subjects with AEs and NOT on the number of AEs.

The analysis of adverse events will be based on the concept of treatment emergent adverse events. AEs occurring from the start of treatment until stop of treatment + residual effect period (REP = 5 days) will be considered on-treatment. AEs occurring prior to the start of treatment will be assigned to 'screening'. AEs occurring after the REP will be assigned to 'post-treatment'.

An overall summary of adverse events will be presented for each study treatment for all treated subjects. This will show the number and percent of patients with any AE, any investigator defined drug-related AE, AEs leading to the discontinuation of study medication, and serious AEs (including reason for serious (death, life-threatening, disability/permanent damage, required or prolonged hospitalization, congenital abnormality/birth defect and other medically important).

The AEs will be coded using the Medical Dictionary for Regulatory Agencies (MedDRA) coding dictionary. The frequency of patients with AEs will be summarised by treatment, primary system organ class and preferred term. A patient with multiple on-treatment occurrences of the same preferred term meeting the criteria for inclusion in the table will be counted only once in these tabulations. Separate tables will be provided for patients with any AE, adverse events leading to discontinuation and serious adverse events. Additional table will present the frequency of patients with AEs by worst severity (mild, moderate, severe). When no events meet the criteria for inclusion in one of these four tables, the table will be shown as indicating no events of that type have occurred.

The system organ classes will be sorted according to the standard sort order specified by EMEA, preferred terms will be sorted by descending overall frequency (within system organ class). The following adverse events of special interest (AESI) have been defined in the protocol. Please refer to section 5.2.6.1.4 Adverse events of special interest in the CTP.

Ocular Safety Assessments

Eye exams including the evaluation of cataract by slit lamp will be performed by an ophthalmologist or an optometrist in both eyes to evaluate the presence or absence of lens disorders and cataract during the screening period. Eye assessments will be performed according to the Eye Examination Worksheet provided by the sponsor. The individual ophthalmological values for all treated subjects will be presented via by-patient listing.

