5.2.6 Assessment of adverse events

5.2.6.1 Definitions of AEs

5.2.6.1.1 Adverse event

An AE is defined as any untoward medical occurrence in a patient or clinical investigation subject administered a medicinal product and which does not necessarily have to have a causal relationship with this treatment.

An AE can therefore be any unfavourable and unintended sign (including an abnormal laboratory finding), symptom, or disease temporally associated with the use of a medicinal product, whether or not considered related to the medicinal product.

The following should also be recorded as an AE in the CRF and BI SAE form (if applicable):

- Worsening of the underlying disease or of other pre-existing conditions.
- Changes in vital signs, ECG, physical examination and laboratory test results, if they are judged clinically relevant by the investigator.

If such abnormalities already exist prior to trial inclusion, they will be considered as baseline conditions and should be collected in the eCRF only.

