5.2.6.2 Adverse event collection and reporting

5.2.6.2.1 AE Collection

The investigator shall maintain and keep detailed records of all AEs in the patient files.

The following must be collected and documented on the appropriate CRF(s) by the investigator:

Clinical Trial Protocol

Proprietary confidential information © 2025 Boehringer Ingelheim International GmbH or one or more of its affiliated companies

- From signing the informed consent onwards until the follow-up visit: all AEs (serious and non-serious) and all AESIs.
- After follow-up-visit 1 until the individual patient's end of trial: cancers of new histology and exacerbations of existing cancer, all trial drug related SAEs and all trial drug related AESIs.
- After the individual patient's end of trial: the investigator does not need to actively monitor the patient for new AEs but should only report any occurrence of cancer and trial treatment related SAEs and trial treatment related AESIs of which the investigator may become aware of by any means of communication, e.g. telephone call. Those AEs should be reported on the BI SAE form (section [5.2.6.2.2](#)), but not on the CRF.

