7.2.6 Safety analyses

Adverse events will be coded using the Medical Dictionary for Drug Regulatory Activities (MedDRA). Standard BI summary tables and listings will be produced. All adverse events with an onset between start of treatment and end of study, which include a 5-day period after last dose of trial medication, will be assigned to the on-treatment period for evaluation.

[figure not shown]
All treated patients (i.e., all patients who received at least one dose of trial medication) will be included in the safety analysis. In general, safety analyses will be descriptive in nature and will be based on BI standards. No hypothesis testing is planned.

Statistical analysis and reporting of adverse events will concentrate on treatment-emergent adverse events, i.e. all adverse events occurring between start of treatment and end of the study. Adverse events that start before first intake of trial medication and deteriorate under treatment will also be considered as 'treatment-emergent'.

Frequency, severity, and causal relationship of adverse events will be tabulated by system organ class and preferred term after coding according to the current version of the MedDRA at the database lock.

Laboratory data will be analyzed both quantitatively as well as qualitatively. The latter will be done via comparison of laboratory data to their reference ranges. Values outside the reference range as well as values defined as clinically relevant will be summarized. Treatment groups will be compared descriptively with regard to distribution parameters as well as with regard to frequency and percentage of patients with abnormal values or clinically relevant abnormal values.

Vital signs, physical examinations, or other safety-relevant data observed at screening, baseline, during the course of the study and at the end-of-study evaluation will be assessed with regards to possible changes compared to findings before start of treatment.

Clinical Trial Protocol

Proprietary confidential information © 2025 Boehringer Ingelheim International GmbH or one or more of its affiliated companies

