3. INTRODUCTION

As per ICH E9 (1), the purpose of this document is to provide a more technical and detailed elaboration of the principal features of the analysis described in the protocol, and to include detailed procedures for executing the statistical analysis of the primary and secondary variables and other data.

This Trial Statistical Analysis Plan (TSAP) assumes familiarity with the Clinical Trial Protocol (CTP) version 5.0 (Dated 08Jan24), including any Protocol Amendment(s). In particular, this TSAP is based on the planned analysis specification as written in CTP Section 7.2. Therefore, TSAP readers may consult the CTP for more background information on the study, e.g., on study objectives, study design and population, treatments, definition of measurements and variables, planning of sample size, randomization.”

SAS® Version 9.4 (or later) will be used for statistical analyses. R version 4.0.2 (or later) with “DoseFinding” package [R15-2001] will be used for analysis based on MCP-Mod.

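### SAP 7.8.1 leaves out the protocol rule that an AE starting before first intake and deteriorating on treatment is treatment-emergent

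*SAP*

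**What the plan says.** Protocol 7.2.6 centres the AE analysis on treatment-emergent events, meaning those occurring from the start of treatment, and then extends the definition: "Adverse events that start before first intake of trial medication and deteriorate under treatment will also be considered as" treatment-emergent.

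SAP 7.8.1 opens with the same idea: "The analysis of adverse events will be based on the concept of treatment emergent adverse events". It then gives three allocation rules:

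- before treatment: "AEs occurring prior to the start of treatment will be assigned to" screening;
- on treatment: "AEs occurring from the start of treatment until stop of treatment + residual effect period (REP = 5 days) will be considered on-treatment";
- after the residual effect period: post-treatment.

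No rule covers an event that begins before first dose and gets worse afterwards. The preferred-term tabulations are described in terms of on-treatment occurrences: "A patient with multiple on-treatment occurrences of the same preferred term meeting the criteria for inclusion in the table will be counted only once". Separate tables are planned for any AE, AEs leading to discontinuation and serious AEs, with a further table by worst severity.

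The SAP introduction states that "this TSAP is based on the planned analysis specification as written in CTP Section 7.2", the part of the protocol that contains the worsening rule. The visible items in SAP section 4, which lists changes to the planned analysis, do not mention it. The visible list begins at item 2, so item 1 cannot be checked.

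**The concern.** The two documents define the on-treatment AE population differently, and the SAP is the one from which tables are programmed. Safety and tolerability against placebo is a stated objective (Protocol 2.1.1) and will be read from arms of about 15.

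Events of the affected kind can be expected in the database. Protocol 5.2.6.2.1 collects "From signing the informed consent onwards until the follow-up visit: all AEs (serious and non-serious) and all AESIs". Screening is planned at up to 30 days and may be extended (Flow Chart A, Protocol 6.2.1), and randomization takes place at least 7 days before first dose (Protocol 4.1.4). An AE still open at first dose is therefore foreseeable.

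If such an event goes from mild to severe on treatment and is filed under screening, the by-arm tables do not show the deterioration. If the drug worsens existing events more often than placebo does, leaving them out pulls the active-versus-placebo comparison toward no difference. If worsening is equally common in all arms, the counts fall but the expected difference does not change.

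**Working it through.** The documents give no figure to reproduce. The check compares the texts and then works out the weight of one patient.

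**Step 1. Does the SAP's period rule already cover worsening?** Protocol 7.2.6 first defines treatment-emergent events as those occurring from the start of treatment, then adds events that start earlier and deteriorate, introduced as a further category. So the protocol did not take a period rule alone to cover worsening. The SAP keeps the period rule and omits the addition.

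**Step 2. Which worsened events are caught by other recording rules?**

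| Situation at first dose | Protocol recording rule | Effect under SAP 7.8.1 as written |
|---|---|---|
| Pre-existing condition worsens on treatment | 5.2.6.1.1 lists as an AE: "Worsening of the underlying disease or of other pre-existing conditions" | Counted when entered as a new AE with on-treatment onset |
| Earlier ECG finding deteriorates | 5.2.4 has deterioration of earlier findings recorded as an AE or SAE | Counted, on the same condition |
| AE that arose between consent and first dose, still open, worsens on treatment | No clear requirement for a second record; 5.2.6.2.2 requires follow-up of AEs until resolved, chronic or stable, which fits keeping one record open | Onset is before treatment, so assigned to screening and not counted |

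The gap is the third row, where the site keeps a single record.

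**Step 3. What does one such patient weigh?** Inputs: 15 patients per arm (Protocol synopsis), and SAP section 7, which bases percentages on all subjects in the set. Assumptions: all 15 are treated, and the patient has no other on-treatment occurrence of the same term.

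Change in an arm's incidence for the term = k / 15, where k is the number of affected patients:

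- k = 0: 0 points
- k = 1: 1/15 = 6.7 points
- k = 2: 2/15 = 13.3 points

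The documents give no value for k. A patient who has another on-treatment occurrence of the same term leaves that term's incidence unchanged.

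**The case against.** The strongest reply is that the SAP is silent and does not contradict the protocol. It speaks of AEs occurring before treatment, not of every AE that began then. It names the treatment-emergent concept, whose only definition in the documents is the protocol's, and it says that it builds on protocol section 7.2. A programmer with both documents could apply the worsening rule. Sponsor standards that are not visible here may also contain it.

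This stands as a limit on certainty. A reader might infer that the SAP withdrew the rule, or that worsening on drug is bound to vanish from the by-arm tables. The documents support neither reading: nothing in the SAP rejects the rule, and one item of its list of changes cannot be seen. The reply does not remove the point. The SAP's stated purpose is to give detailed procedures for carrying out the analysis, and its explicit allocation, followed literally, gives a different count from the protocol's rule. Two programmers could produce different tables.

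The second reply is that the signals of most interest are reported elsewhere. The SAP plans on-treatment laboratory abnormalities and maximum ALT, AST and bilirubin plots (7.8.2), ECG summaries and listings (7.8.4), by-patient eye listings (7.8.1) and AE listings for all subjects (section 7). Entry criteria also remove marked QTcF prolongation, ALT or AST above three times the upper limit, and graded cataract above the stated limit. This largely stands. It would be wrong to conclude that QT, liver or lens signals would be hidden. What those displays do not supply is the by-arm count of symptomatic AEs, their worst severity, and discontinuations due to an AE.

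Third, AE analyses are descriptive with no hypothesis testing, so no formal inference is affected. That is correct and bears on the weight of the point.

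**Conclusion.** SAP 7.8.1 omits a rule that Protocol 7.2.6 states, and no visible item in SAP section 4 records the omission. Applied as written, its allocation leaves out of the on-treatment tables any AE that first arose between consent and first dose, was kept under its original record, and deteriorated on treatment. The preferred-term, worst-severity, serious and discontinuation tables are all exposed to this.

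The loss is confined to that group. Its size is unknown and may be zero; under the assumptions in the working, each affected patient is worth 6.7 points for the term in an arm of 15. A shift toward no difference arises only if worsening is more common on drug than on placebo. The conclusion also rests on sites not opening a new record when such an AE worsens, and on tables being programmed from the SAP wording alone. It is a limited inconsistency in an exploratory trial, worth correcting because the repair is specific and nearly free.

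**What to change.** In SAP 7.8.1, replace the screening rule with wording such as: *An AE with onset before first intake is assigned to screening unless it deteriorates between first intake and stop of treatment + 5 days; in that case it is counted as on-treatment, in line with CTP 7.2.6.* Add a sentence saying how deterioration is identified from the recorded AE data.

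If the departure from the protocol is intended, list it in SAP section 4 with the reason.

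The change should go no further than the protocol rule. Adding a criterion such as becoming serious would exceed Protocol 7.2.6, and an instruction to sites to split records is not needed for this repair.

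The cost is a sentence or two of SAP text and the matching programming. The downside is slightly higher AE counts in all arms, including placebo.
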